6 ETHICAL REQUIREMENTS

6.1 Ethical Authorisation

The Clinical Investigation Plan will be submitted to the relevant Ethics Committee for approval.

6.2 Amendments to the Clinical Investigation Plan

Any amendments to this Investigation Plan will be submitted by the Sponsor, in the form of an amendment, to the relevant Ethics Committee for approval.

6.3 Information to the Subject

The purposes and modalities of the Investigation will be explained to each subject by means of an information document (Informed Consent), containing what is verbally stated by the clinician. The subject must date and sign the consent document.

A copy of the document will be given to the subject while the original will be kept by the investigator.

6.4 Adverse Events

An Adverse Event is defined as any harmful clinical event that will occur during the course of the clinical investigation in one of the subjects comprising the study population who has undergone one of the treatments in the investigation plan.

Adverse events will be classified into serious (SAE) non-serious (AE) and Suspected Serious and Unexpected Adverse Reactions (SUSAR).

An Adverse Event is defined as serious if (ICH-GCP DM 15/07/1997):

- it causes the death of the subject involved in the investigation
- places the subject's life in danger
- is such as to require hospitalization
- is such as to require prolonged hospitalization
- is such as to cause permanent or temporary disability
- leads to a congenital anomaly or birth defect

In all other cases, the Adverse Event will be non-serious and will be classified as:

- *mild* does not interfere with normal activities of daily living and resolves spontaneously.

- *moderate*, interferes with activities of daily living but resolves spontaneously;
- *severe*, prevents daily life activities and does not resolve spontaneously.

All personnel who come in contact with study subjects must report Adverse Events reported by subjects to the Investigator, who has a duty to collect all possible data about them.

- Adverse events (AEs) will be reported within 48 h by the Principal Investigator to the Clinical Research Unit of Guna S.p.a, through telephone, email, appropriate form and simultaneously through e-CRF.
- Serious Adverse Events (SAEs) and Suspected Serious and Unexpected Adverse Reactions (SUSARs) will have to be reported to the Sponsor immediately (within 24 h maximum) through telephone, email, appropriate form and simultaneously through e-CRF by the Principal Investigator and communicated to the Ethics Committee and the Ministry of Health.

Unità di Ricerca Clinica di GUNA S.p.a.

[contact]

mail: [contact]

[contact]

[contact]

Ufficio Farmacovigilanza di GUNA S.p.a.

[contact]

mail: [contact]

[contact]

The investigator should ensure that procedures are in place to ensure that the event is resolved.

In the case of nonserious Adverse Events (AEs), it is necessary to keep in mind that they can still give rise to serious events, which is why each Adverse Event must be monitored.

Adverse Events that have not yet resolved at the end of the study will be followed up by the Investigator; each subject who has experienced an Adverse Event will be contacted at least once a month after the conclusion of the study for as many months as deemed appropriate.

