4.9.2 Plan Visits

T0 BASAL: Enrollment

During the daily clinical activity, investigators participating in the Investigation will select subjects with rotator cuff syndrome. The Principal Investigator will be responsible for the correct clinical diagnosis by also making use of the instrumental examinations provided in the Investigation Plan. Subjects meeting the selection criteria will thus be identified. After fully explaining the purposes, aims and procedures stipulated in the Clinical Investigation Plan, the subject will be offered participation in the Clinical Investigation Plan itself. Finally, the selected subject will be asked to review the information form and to date and sign the Informed Consent and Consent to Processing of Personal Data form.

Female subjects will need to provide evidence of a negative pregnancy test in order to be enrolled.

We will then proceed with the objective examination and collection of the information required by the appropriately prepared Electronic Data Collection Form.

This will be followed by:

- CMS assessment;
- NRS assessment;
- ASES assessment.
- SST evaluation;
- shoulder ROM evaluation;
- MRI evaluation.

The first infiltration will then be performed via ultrasound.

Previous or ongoing pharmacological treatments of any kind will be documented.

In order to monitor the consumption of analgesic (Celecoxib 200mg / Paracetamol 1000 mg) used during the Clinical study in case of pain onset, a clinical diary will be given to the subject in which to indicate the day and dose of medication used.

The enrolled subject will be given the identification code formed by the progressive enrollment number followed by an alphanumeric code.

T2 week (±2 days):

At 14 days from day 0 (enrollment), the second infiltration will be performed through echoguide and pain assessment through NRS, finally painkiller drug use will be evaluated through clinical diary analysis, and any Adverse Events occurred after the first administration will be assessed.

T4 weeks (±2 days):

At 28 days from day 0 (T4w), the third ultrasound-guided infiltration and pain assessment through NRS will be performed, finally painkiller drug use will be assessed through clinical diary analysis and any Adverse Events occurred after the last administration will be evaluated.

T3 months (±7 days):

At 3 months from day 0 and at 2 months from the last echoguided administration, the End Points in the Clinical Investigation Plan will be assessed.

Including:

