5.2.3 Secondary End Points

Secondary End Points will consist of evaluating the efficacy, in terms of performance, of MD-Shoulder *Collagen Medical Device* through:

- CMS at months 3, 6 and months 12 compared to day 0, using ANOVA with repeated measures within patient, or Friedman's test.
- NRS at week 2, week 4, months 3, months 6, months 12 compared to day 0 using ANOVA with repeated measures within patient, or Friedman's test.
- ASES and SST at day 0, months 3, months 6 and months 12 using ANOVA with repeated measures within patient, or Friedman's test.

- cuff integrity at day 0 and months 12 by performing MRI of the treated shoulder using Clopper-Pearson binomial test.
- analgesic consumption in the various phases of the study, understood as dosage units/month and evaluated as mean, CI 95% of mean, median, CI 95% of median, SD and range.
- adverse events by records of the various AEs, SAEs, SUSARs according to § 6.4.

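### The section 6.4 grades for non-serious adverse events leave 3 of 6 combinations of interference and resolution without a grade (2 of 6 on a broader reading): a minor wording fix

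*Combined protocol and SAP*

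**What the plan says.** Section 6.4 first separates serious from non-serious events by a list of criteria. It then says of everything else: "In all other cases, the Adverse Event will be non-serious and will be classified as" one of three grades.

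- The lowest grade, mild, is for an event that "does not interfere with normal activities of daily living and resolves spontaneously".
- The middle grade, moderate, is for one that "interferes with activities of daily living but resolves spontaneously".
- The top grade, severe, is for one that "prevents daily life activities and does not resolve spontaneously".

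Section 6.4 does not define spontaneous resolution, does not say when the grade is assigned, and gives no rule for an event that meets none of the three definitions. It does require AEs to be monitored, and it provides for contact at least monthly after the study for subjects who have had an AE.

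Safety is part of the study purpose (section 3.2), and AE evaluation is a listed secondary endpoint (section 4.13.3). Section 5.2.3 plans to report "adverse events by records of the various AEs, SAEs, SUSARs according to § 6.4".

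**The concern.** A grading scale that must be applied to every non-serious AE should give each possible event exactly one grade. Here each definition sets two conditions at once, and the conditions can vary independently. An event can interfere with daily life and fail to resolve by itself, or prevent daily activities and pass without treatment. Neither fits a definition as written.

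Such events are plausible in this study. Subjects receive three infiltrations, and section 4.9.2 monitors "consumption of analgesic (Celecoxib 200mg / Paracetamol 1000 mg) used during the Clinical study in case of pain onset". Suppose pain after an infiltration is recorded as an AE, limits activity, and ends with that analgesic. If spontaneous resolution means ending without treatment, the event is not moderate, because it did not resolve by itself. It is not severe either, because it did not prevent activities. The investigator could call it moderate by its interference or severe by its resolution. On the same assumption, giving an analgesic can take an event out of its grade with no change in intensity.

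What is at stake is the consistency of the severity description of non-serious AEs, in a study that states safety as an objective.

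**Working it through.** The documents state no figure on this point, so there is none to reproduce. The check enumerates the definitions.

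Inputs, all from section 6.4: three levels of interference (none, interferes, prevents) and two resolution states (spontaneous, not spontaneous). Combinations: 3 × 2 = 6.

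| Interference | Resolves spontaneously | Does not resolve spontaneously |
|---|---|---|
| None | mild | no grade |
| Interferes | moderate | no grade |
| Prevents activities | no grade | severe |

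**Literal reading.** Graded: 3. Ungraded: 6 − 3 = 3, that is 3/6 = 50% of combinations.

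**Other readings.**

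1. Interference includes prevention. An event that prevents activities and resolves by itself is then moderate. Ungraded: 2/6 = 33%. The text uses the two words for different grades, so separate levels are the more natural reading.
2. Prevention of activities counts as the serious criterion "is such as to cause permanent or temporary disability". The two cells in the last row become serious events, the severe grade is empty, and 6 − 2 = 4 combinations remain. Two are graded, and 2/4 = 50% are not. This reading is less likely, because a severe grade among non-serious events implies that the plan expects some of them to prevent activities.
3. Spontaneous resolution means only that the event resolves, with or without treatment. The analgesic example then falls away, but the grid has the same shape and 3/6 remain ungraded.

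Two combinations lack a grade under all four readings: no interference without (spontaneous) resolution, and interference without (spontaneous) resolution.

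**After the fix.** With grades set by interference alone, each row has one grade whatever the resolution state: 6/6 graded, 0 ungraded.

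**The case against.** The strongest reply is that nothing planned depends on the grade. Section 5.2.3 refers to AEs, SAEs and SUSARs, which are seriousness classes, and names no table by grade. The 48 h and 24 h reporting limits turn on seriousness, and the split between serious and non-serious has no gap. Early withdrawal (section 4.15) and premature termination do not mention grade. The study has one arm and 24 subjects, with descriptive AE reporting, so no comparison between arms can be distorted. All of this stands, and it is why the point is minor.

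It is also fair that the analgesic example is conditional: the pain must be recorded as an AE, and the undefined term must mean ending without treatment. Pain scores, the analgesic diary and concomitant treatment are recorded separately, so much of the information on treatment would be recoverable. The AE form and the e-CRF are not in the documents and may already hold outcome and date.

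A reader might infer that an event still open when first reported cannot be graded at all, because "Adverse events (AEs) will be reported within 48 h by the Principal Investigator". The documents do not support that. The rule sets a deadline for reporting, not for a final grade, and with monitoring and contact after the study a grade can be given or revised once the outcome is known. The difficulty remains only for events still unresolved when follow-up stops.

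What the reply does not remove is the gap itself. Section 6.4 makes the classification mandatory, and no reading considered here makes it complete.

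**Conclusion.** The point holds as a minor defect of definition. As written, the grades leave 3 of 6 combinations uncovered, or 2 of 6 if interference includes prevention, with no fallback. Events in those combinations would be graded by individual judgement, so the severity description of non-serious AEs could be inconsistent.

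A reader might infer that half of the AEs would go ungraded, or that the safety evaluation is compromised. Neither follows. The 50% counts cells in a grid of definitions, and the plan gives no expected AE rate from which to count events. Seriousness classification, reporting deadlines, follow-up and the primary CMS analysis do not use the grade.

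The count rests on treating interference and prevention as separate levels. The analgesic example, but not the count, rests on reading spontaneous resolution as ending without treatment.

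**What to change.** In section 6.4, define the three grades by interference only: mild if the event does not interfere with daily activities, moderate if it interferes with them, severe if it prevents them. State that the grade is the worst level reached, given at first report and updated if the event worsens. Record the outcome (resolved spontaneously, resolved with treatment, or ongoing) and its date as separate e-CRF items, if they are not already there. Leave the provision for contact after the study as it is.

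The cost is three reworded lines and two added sentences, submitted as an amendment under section 6.2, and at most two e-CRF fields. The downside is slightly more data entry per AE. No visit, endpoint, test or sample size changes. Where the present grades are defined, they can still be rebuilt from grade plus outcome.

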5.4. Privacy Protection

The identities of data subjects will be known only to the Investigators and the Clinical Monitor in charge of monitoring the investigation. Reference will be made to Regulation (EU) 2017/745.

Full respect for the anonymity of the subjects participating in the Clinical study will be ensured. Data collection, data processing, any scientific publications or congress presentations of the results of the Clinical Investigation will be conducted in accordance with the current Privacy Law - Regulation (EU) 2017/745.

6.5 Access to data

In compliance with the regulations in force concerning Clinical Investigations on medical devices, the Institute and the investigators will allow monitoring of the study according to the monitoring plan drawn up by the Sponsor. In addition, they will allow the Competent Authorities direct access to the study documentation being audited.

6.6 Data ownership

All data collected will belong to Guna S.p.a. Milan, Italy, Sponsor of the Clinical study.
Further information on data ownership can be found in the Economic Agreement document.

6.7 Data processing and publication

The results of this study will be summarised and presented in a final report that will aim to draw reliable conclusions regarding the clinical efficacy of the infiltrative treatment of rotator cuff syndrome by means of an infiltrative cycle with MD-Shoulder *Collagen Medical Device* injectable. The scientific article will then be edited and sent to a peer reviewed journal in the field for publication in order to disseminate the results obtained to the scientific community.

6.8 Funding

This research is financed by GUNA S.p.a.
Please refer to the Economic Agreement for further information.

6.9 Code of Ethics

Reference is made to the Declaration of Helsinki (Fortaleza 64th 2013) and the principles of Good Clinical Practice (GCP) are to be followed (D.leg. 24 June 2003 - n.211 in G.U. n.184 of 09/08/2003).

6.10 Subject Insurance

Insurance cover will be provided by GUNA S.p.a. for the entire duration of the clinical investigation project for all subjects enrolled.

5. PREMATURE TERMINATION OF THE CLINICAL INVESTIGATION

The Investigators reserve the right to discontinue the investigation at any time for reasonable medical and/or administrative reasons. Reasons for discontinuation will be documented; the Ethics Committee and the Ministry of Health will be informed of the decision.

7 GLOSSARY

Medical device: Any instrument, apparatus, implant, substance or other product, whether used alone or in combination, including computer software used for proper functioning, and intended by the manufacturer for use in man for the purpose of diagnosis prevention, control, therapy or mitigation of a disease; diagnosis, control, therapy, mitigation or compensation for an injury or handicap of study, replacement or modification of anatomy or a physiological process; of intervention in conception, which product does not exert its principal action, in or on the human body, for which it is intended, by pharmacological or immunological means, nor by metabolic process but whose function may be assisted by such means.

8 ATTACHMENTS TO THE INVESTIGATIONAL STUDY PLAN

- A. Informed Consent (disclosure and consent)
- B. Consent to the processing of personal data (information and consent)
- C. Clinical diary
- D. Constant-Murley Score (CMS)
- E. Numeric Rating Scale (NRS) - American Shoulder and Elbow Surgeons (ASES) –
Simply Shoulder Test SST
- F. Range Of Motion (ROM) of shoulder

